3.3 Study Duration, Enrollment and Number of Sites

3.3.1 Duration of Study Participation

Total study duration is 18 months, including 6 months of a treatment phase and 12 months of a follow-up phase.

3.3.2 Total Number of Study Sites/Total Number of Subjects Projected

All testing procedures and interventions will occur in the Center for Rehabilitation at CHOP. Sixty participants with CP between the ages of 1-3 years will be recruited for the study. It is expected that enrollment of 60 participants will produce 42 evaluable datasets.

3.4 Study Population

3.4.1 Inclusion Criteria

- 1) 12-36 months of age
- 2) Gross motor function below the 10th percentile for age (Bayley Scales of Infant and Toddler Development, BSID-III, corrected for gestational age, if applicable, under the age of two years).
- 3) Diagnosis of CP or neurological sign associated with CP (i.e. spasticity).
- 4) Ability to initiate pulling to stand at a surface (Score of 1 on GMFM Item 52).
- 5) Cognitive ability to follow one-step commands.

3.4.2 Exclusion Criteria

- 1) Secondary orthopedic, neuromuscular or cardiovascular condition unrelated to CP.
- 2) General muscle hypotonia, without other neurological signs associated with CP.
- 3) Independent walking ability (Score of 3 on GMFM Item 69 – Walks forward 10 steps).
- 4) At or above the 50th percentile of GMFCS Level I.
- 5) History of surgery or injury to the lower extremities in the past 6 months.

Subjects that do not meet all of the enrollment criteria may not be enrolled. Any violations of these criteria must be reported in accordance with IRB Policies and Procedures.

4 STUDY PROCEDURES

Please refer to table 1 “Schedule of study procedures”

4.1 Screening Visit

- Informed Consent
- Physical Therapy Examination
- Medical Record Review
- BSID-III, gross motor scale
- Review of Inclusion and Exclusion criteria

4.2 Treatment Phase

4.2.1 Assessment sessions 1-5

- Randomization (Assessment 1 only)
- Weight
- Gross motor function (GMFM-66)
- Secondary outcomes (Postural control, physical activity, caregiver satisfaction, Child Engagement in Daily Life)
- BSID-III, cognitive scale (Assessments 1 and 5)
- Family Empowerment Scale (Assessments 1 and 5)
- Possible video or photograph

4.2.2 Treatment sessions 1-72

- Rehabilitation (three 30-minute sessions per week of either DSM or CONV treatment)
- Possible video or photograph

4.3 Follow-up Phase

4.3.1 Follow-up assessments (3, 6 and 12 months)

- Gross motor function (GMFM-66)
- Secondary outcomes (Postural control, physical activity, caregiver satisfaction, Child Engagement in Daily Life)
- BSID-III, cognitive scale (6 and 12 month follow-ups)
- Family Empowerment Scale (6 and 12 month follow-ups)

- Possible video or photograph

4.4 Subject Completion/Withdrawal

Subjects may withdraw from the study at any time without prejudice to their care. Intent to treat procedures will be followed such that participants will not be withdrawn from the study by the investigators for lack of adherence to the treatment schedule. Participants will not be withdrawn from the study for missing treatment sessions. The Investigator or the Sponsor (if applicable) may also withdraw subjects who violate the study plan, or to protect the subject for reasons of safety or for administrative reasons. It will be documented whether or not each subject completes the clinical study. If the Investigator becomes aware of any serious, related adverse events after the subject completes or withdraws from the study, they will be recorded in the source documents and on the CRF.

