3.1.2 Study Treatment Phase (start of the study intervention)

Children will be able to continue their outside therapies, if their families' choose to do so. Whether they reduce or continue their pre-enrollment therapy schedule, families will be asked to maintain the schedule of outside physical therapy constant throughout the treatment phase. It is anticipated that most children will be receiving early intervention therapy services in the home. Other medical care will be documented but not restricted. If parents sign CHOP's standard HIPAA authorization, we will request copies of outside therapy notes to assist with documentation of co-occurring treatments. Treatment will start within one week of Assessment 1 and will be delivered by the primary or secondary research physical therapist, both of whom will be trained using the study manual to provide each type of treatment. We will follow intent to treat procedures such that no child will be withdrawn from the study for failing to adhere to the therapy schedule. A training log will be maintained for each session. One session per week will be videotaped (if separate consent is provided) for quality control to ensure that activities between the treatments remain different and are consistent with the distinguishing characteristics.

After enrollment and the initial assessment, participants will be randomized to receive either DSM or conventional (CONV) treatment, using a randomization scheme to ensure that motor ability does not differ at baseline. Participants will also be randomly assigned to either the primary or secondary research therapist who will each provide both

types of treatments, to minimize any differences related to individual therapist. Treatment in both groups will occur at an intensity of 3 times per week for 30 minutes.

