3.1.3 Follow-up Phase

The treatment phase will end after 24 weeks of treatment. Three follow-up assessments will occur at 3, 6 and 12 months after treatment ends.

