4.4.1 Early Termination Study Visit

Subjects who withdraw from the study will have all procedures enumerated for Assessment 5 completed as the early termination visit.

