8.1.2 Blinding

A blinded assessor will collect all outcomes measures. Blinding of participants to treatment group is not feasible with the proposed interventions.

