8.4 Regulatory and Ethical Considerations

8.4.1 Data and Safety Monitoring Plan

The incidence of adverse events is expected to be low in this single-site minimal risk research. The PI will be responsible for monitoring the data and safety of all participants. All study procedures will receive IRB approval prior to recruitment or enrollment of participants. In addition to the data management procedures outlined above, the PI will hold biweekly study team meetings to evaluate the safety and progress of all research procedures. Standard procedures for all data collection methods will be reviewed at the start and periodically throughout the study. Data checks for errors will be performed prior to analysis. Training log review and random video checks will be conducted regularly to ensure that the rehabilitation programs are delivered as intended. The PI will be actively involved in reviewing the progress of each study participant and will bring to the attention of the IRB adverse events and unexpected problems. Unexpected safety concerns will also be communicated with the NINDS Program Official in accordance with study regulations.

Additionally, if we experience adverse events in more than 15% of total participants, we will appoint a Study Monitoring Committee to review the safety events that occurred and monitor safety for the remaining duration of the study.

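### Section 4.4 lets the Investigator or Sponsor remove randomised children from the study on undefined grounds, and nothing provides for assessing them after one early-termination visit

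*Combined protocol and SAP*

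**What the plan says.** Section 3.1.2 gives the promise: "We will follow intent to treat procedures such that no child will be withdrawn from the study for failing to adhere to the therapy schedule". Section 4.4 repeats it: "Intent to treat procedures will be followed such that participants will not be withdrawn from the study by the investigators for lack of adherence". It then adds: "Participants will not be withdrawn from the study for missing treatment sessions". So intent-to-treat is described only in terms of attendance and adherence to the therapy schedule.

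The same paragraph of 4.4 goes on: "The Investigator or the Sponsor (if applicable) may also withdraw subjects who violate the study plan". Safety and administrative reasons are listed as further grounds. Neither a study-plan violation nor an administrative reason is defined.

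On what follows withdrawal, section 4.4.1 says: "Subjects who withdraw from the study will have all procedures enumerated for Assessment 5 completed as the early termination visit". Section 4.2.1 shows that Assessment 5 includes the GMFM-66. The normal schedule continues well beyond that point. Section 3.1.3 states: "Three follow-up assessments will occur at 3, 6 and 12 months after treatment ends".

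On blinding, section 8.1.2 says: "A blinded assessor will collect all outcomes measures. Blinding of participants to treatment group is not feasible with the proposed interventions". No blinding is stated for the Investigator or the Sponsor. Section 8.4.1 says: "The PI will be actively involved in reviewing the progress of each study participant", and provides for regular training-log review and random video checks.

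Section 6.2.2 plans an ANCOVA at each time point, plus a mixed model or GEE. Section 6 defines no analysis set.

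**The concern.** Randomisation protects the comparison only if randomised children stay in it for reasons unrelated to how they respond. Here the people running the trial may end a child's participation after randomisation on open-ended grounds. Ending participation also ends outcome collection, apart from one visit. If those decisions happened to track both arm and response, the children still measured at 24 weeks and at follow-up would no longer be the groups that were randomised.

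Hypotheses 1.1 and 2.2 both include maintenance at follow-up, and those are the visits such children would miss. With about 21 children per arm in the sample-size section, each lost child carries weight.

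**Working it through.** **Which departures are protected.** Poor adherence to the therapy schedule and missed sessions cannot lead to withdrawal (3.1.2, 4.4). Any other departure from the plan, and any administrative reason, can (4.4). The clause is therefore a residual category, but one without limits.

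**Which data are lost.** Read as covering children withdrawn by the Investigator or Sponsor as well as by families, 4.4.1 yields one GMFM-66 at whatever time the child leaves. Any remaining treatment-phase assessment and the 3, 6 and 12 month visits are not provided for. The termination value does not stand in for a 24-week value: section 6.3 itself assumes that the DSM gain doubles between 6 weeks and 12 or more weeks. Section 6.2.2 has no rule for placing an off-schedule value.

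**What each analysis does.**
- The per-visit ANCOVA uses only children measured at that visit, so a withdrawn child drops out of every later one.
- The likelihood-based mixed model keeps the recorded scores and can account for withdrawal that depends on them. It does not remove bias if withdrawal depends on outcomes beyond those recorded.
- GEE also keeps the recorded data but, without weighting, needs a stronger assumption about why data are missing.

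**The plan's own precision (6.3).** With 17 per arm and SD 9, the half-width is 1.96 × 9 × √(2/17) = 6.05. The stated 6 reproduces. The predicted difference is 10.6 − 1.8 = 8.8.

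**Illustration of size.** The documents give no expected number of such withdrawals, so these are assumptions: k children are lost from one arm only, each would have changed by 9 points (one SD) less than the full arm mean, and no outcome from them is used. With N children per arm, the mean of those remaining is higher than the full arm mean by 9k/(N − k).

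| N per arm | k = 2 | k = 3 |
|---|---|---|
| 21 (section 6.3) | 18/19 = 0.95 | 27/18 = 1.5 |
| 30 (half of the 60 in section 3.3.2) | 18/28 = 0.64 | 27/27 = 1.0 |

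Both sizes are shown because 6.3 works with 42 children and 3.3.2 enrols 60. If the 9 points were measured from the children who remain, the formula would be 9k/N, which gives 0.86 and 1.29 for N = 21.

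For N = 21, a shift of 0.95 is 0.95/8.8 = 11% of the predicted difference and 0.95/6 = 16% of the planned half-width. A shift of 1.5 is 17% and 25%.

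**Upper bound.** If the k children lost were always the k poorest responders in the arm, simulation with normal outcomes and SD 9 gives average shifts of about 1.6 points for k = 2 and 2.3 for k = 3 with 21 per arm (1.2 and 1.7 with 30).

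**The case against.** The strongest reply is that the clause is narrow. The commonest departures, missed sessions and poor adherence, are expressly protected, and section 4.4.2 even offers make-up sessions. A GMFM-66 is collected at termination and the mixed model keeps it. If withdrawal follows progress already captured in recorded scores, that model deals with much of the problem. The trial is an exploratory proof of concept sized for estimation, and the illustrated shifts are small beside a half-width of 6.

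Much of this stands, and it rules out several stronger readings that a reader might infer:

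- **That unblinded staff will remove children selectively.** The documents do not state whether the Investigator or Sponsor is blinded. Log and video review makes knowledge of the arm plausible, but nothing links it to withdrawal decisions. The sentence about reviewing each child's progress goes on to adverse events and unexpected problems, so it describes safety oversight.
- **That a change in outside therapy is a violation.** Section 3.1.2 asks families to keep outside physical therapy constant. No text calls a change a violation or a ground for withdrawal. Because the term is undefined, such a reading is merely not excluded.
- **That assessment stops at once.** It does not; 4.4.1 requires a full visit.

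What the reply does not answer is that the grounds are open-ended, that no assessment is provided for after the termination visit, and that the per-visit ANCOVAs drop the child. Nor does a wide confidence interval excuse bias, since the interval does not account for it.

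**Conclusion.** The point holds as a gap between the intent-to-treat promise and the withdrawal rule, and it should be closed. The plan permits discretionary removal from the study after randomisation and ties it to the end of outcome collection. Selective loss by arm is a permitted risk, not a demonstrated event.

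Under the one-sided assumptions above, the illustrated shift is 0.64 to 1.5 points. That is modest against a predicted difference of 8.8 and could not by itself produce a difference of that size. It would matter more if the true difference were much smaller than predicted. The shift would be smaller if losses fell in both arms, if the children lost were closer to the arm mean, or if their recorded scores were used.

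**What to change.** - In 4.4 and 4.4.1, separate stopping study treatment from leaving the study. State that a child taken off treatment by the Investigator or Sponsor, for any reason, is still invited to all remaining scheduled assessments, including the three follow-ups, unless the family withdraws consent.
- In section 6, state that all randomised children are analysed in their assigned arm.
- Record and report withdrawals by arm and by reason. Section 4.4 at present requires only a record of whether each child completes.

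The cost is protocol wording and a few more visits for children who are off treatment, within the 8 assessments per child already planned (8.7.2). The rules for stopping treatment itself are not changed.

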4.4.1 Early Termination Study Visit

Subjects who withdraw from the study will have all procedures enumerated for Assessment 5 completed as the early termination visit.

4.4.2 Make-up treatment sessions

If subjects miss greater than 20% of therapy sessions, they will be given the option to make up treatment sessions at the end of the study, after Assessment 5 (at 24 weeks). If six or more make-up sessions are completed, a final post-treatment visit will be completed, which will include a repeat of all procedures enumerated for Assessment 5.

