5.2.4 Bayley Scales of Infant and Toddler Development, cognitive scale

The cognition age equivalent obtained from the BSID-III will be used as a covariate as patient cognition is known to influence response to rehabilitation.^{56,57} To avoid a learning effect from repeated testing, this will be completed only every 6 months.

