5.2.5 Family Empowerment Scale

One caregiver of each participant will complete the Family Empowerment Scale to obtain a measure of the caregiver's self-efficacy, also known to influence response to

rehabilitation.⁵⁸ To avoid caregivers remembering their prior responses, this will be completed only every 6 months.

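### The make-up visit repeats the BSID-III cognitive scale and the Family Empowerment Scale sooner than the six-month spacing the plan sets for them

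*Combined protocol and SAP*

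**What the plan says.** Section 4.4.2 covers children whose missed sessions exceed 20% of the total. The offer made to them reads: "they will be given the option to make up treatment sessions at the end of the study, after Assessment 5 (at 24 weeks"). Once six such sessions have been completed, "a final post-treatment visit will be completed, which will include a repeat of all procedures enumerated for Assessment 5".

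Section 4.2.1 lists what is done at Assessments 1 to 5. Two entries apply to the first and last of these only: "BSID-III, cognitive scale (Assessments 1 and 5") and "Family Empowerment Scale (Assessments 1 and 5"). Both scales are therefore Assessment 5 procedures.

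The measurement sections limit how often each may be given. For the cognitive scale, section 5.2.4 says: "To avoid a learning effect from repeated testing, this will be completed only every 6 months". For the empowerment scale, section 5.2.5 says: "To avoid caregivers remembering their prior responses, this will be completed only every 6 months".

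The follow-up schedule in section 4.3.1 respects the limit: "BSID-III, cognitive scale (6 and 12 month follow-ups") and "Family Empowerment Scale (6 and 12 month follow-ups"). Neither scale is listed for the 3-month visit.

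**The concern.** Staff at a make-up visit cannot follow both instructions unless the visit happens to fall six months or more after Assessment 5. The spacing rule is deliberate. It explains why both scales are left out at Assessments 2 to 4 and at the 3-month follow-up. Its stated reasons, practice on the test and memory of previous answers, apply with more force to a repeat after a few weeks.

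At stake are the scores of a subgroup of children. The repeat score is directly exposed. The 6- and 12-month scores may be too, because the child or caregiver has then met the scale once more, and more recently, than scheduled. Cognition is named in section 2.2 as something to compare between the treatment groups. Otherwise the two measures serve as covariates: 5.2.4 says so for cognition, and 6.2.2 for cognition and caregiver self-efficacy.

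**Working it through.** **Inputs from the documents.** Three sessions a week, numbered 1 to 72 (4.2.2). A 24-week treatment phase (3.1.3). Make-up sessions offered above 20% missed, placed after Assessment 5 at week 24, with the repeat visit triggered by six completed (4.4.2). Both scales scheduled at Assessments 1 and 5 and at the 6- and 12-month follow-ups (4.2.1, 4.3.1).

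**Assumptions.** The plan gives neither a pace nor a cap for make-up sessions. I take one to three a week (three is the protocol's treatment rate), starting directly after Assessment 5, with the visit directly after the last session.

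**Check of the plan's own figure.** 3 sessions a week × 24 weeks = 72, as stated.

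**Who qualifies.** 0.20 × 72 = 14.4, so at least 15 sessions must be missed. Fifteen is the least that qualifies a child, not a ceiling on what can be made up.

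**Gap from Assessment 5 to the repeat.** Weeks = make-up sessions ÷ sessions per week.

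| Make-up sessions | 3 a week | 2 a week | 1 a week |
|---|---|---|---|
| 6 | 2 weeks | 3 weeks | 6 weeks |
| 15 | 5 weeks | 7.5 weeks | 15 weeks |

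Thirty sessions at three a week would take 30 ÷ 3 = 10 weeks.

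**When the spacing would be kept.** The plan's own interval between Assessments 1 and 5 is 24 weeks. To reach it, a child would need 24 × 3 = 72, 24 × 2 = 48 or 24 × 1 = 24 make-up sessions at the three paces. At three a week that is the whole course of treatment.

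**Gap from the repeat to the next scheduled test.** Suppose follow-up is timed from week 24 and six months is counted as 24 weeks.

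- After six sessions: 24 − 6 = 18 to 24 − 2 = 22 weeks.
- After 15 sessions: 24 − 15 = 9 to 24 − 5 = 19 weeks.
- With six months as 26 weeks, add 2: 20 to 24 weeks, and 11 to 21 weeks.

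**Number of administrations per scale.** Scheduled: Assessments 1 and 5 plus 6 and 12 months = 4. With the make-up visit: 5.

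**How many children.** The documents do not allow an estimate. In the five-child pilot the lowest attendance was 81% (1.3), so 100 − 81 = 19% missed, under the 20% trigger, and nobody would have qualified. That treatment phase lasted six weeks, against 24 here.

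**Where the make-up visit enters the analysis.** The ANCOVA list in 6.2.2 names weeks 6, 12, 18 and 24 and the follow-up points, but not this visit. Section 6.1 defines the primary endpoint over every post-treatment assessment session, and the mixed model or GEE has no closed list of visits. Whether the make-up visit is used is therefore not stated. Nor does the plan say which administration of the two scales supplies the covariate.

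**The case against.** The best defence is that the provisions can be reconciled. Sections 5.2.4 and 5.2.5 may govern routine scheduling, while 4.4.2 is a specific clause for an unscheduled visit. Section 4.4.1 prescribes the same full battery at early termination, which can also fall within six months of Assessment 1, so complete end-of-treatment data may be intended. This is possible, but nothing in 4.4.2 waives the spacing rule, and the reasons given for the rule apply fully to a repeat after 2 to 6 weeks. Early termination is also a different case: it may be the only end-of-treatment record for a child who withdraws, whereas a child at the make-up visit already has Assessment 5.

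Four further points stand.

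- Table 1, to which section 4 refers, could not be read and might carry an exemption. If it does, 4.4.2 only needs aligning with it.
- The timing rests on an assumed pace.
- The documents give no size for a learning or recall effect, so carry-over to the follow-up scores is a possibility and no more.
- The Family Empowerment Scale is not named as a secondary outcome, and cognition is absent from the secondary measures described in 5.2.2.

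A reader might infer that the two extra tests serve no analysis at all. The documents do not support that. The endpoint definition in 6.1 and the open visit structure of the mixed model or GEE leave room for the make-up visit, and scores taken there could act as concurrent covariates for the repeat GMFM-66.

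**Conclusion.** The conflict is real in the readable text, and its consequence is small. At one to three make-up sessions a week, the repeat comes 2 to 6 weeks after Assessment 5 at the six-session trigger and 5 to 15 weeks after for 15 sessions, against the 24 weeks between Assessments 1 and 5. It affects only children who miss at least 15 sessions and make up at least six. Their number is unknown and probably small.

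A reader might go further and infer that the primary result is compromised. The documents do not support that. Assessment 5 scores precede the repeat, the GMFM-66 is not under the six-month rule, and if baseline cognition and empowerment values are the covariates, the repeat does not enter the GMFM-66 models. Nothing here changes the half-width of 6 points given in section 6.3. What remains is avoidable exposure of the repeat scores, and possibly of the 6- and 12-month scores, to effects the plan itself sets out to prevent. This is a wording correction worth making, not a flaw in the design.

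**What to change.** In 4.4.2, after the requirement to repeat the Assessment 5 procedures, add: *except the BSID-III cognitive scale and the Family Empowerment Scale*. In 6.2.2, state that any GMFM-66 analysis using the make-up visit takes the Assessment 1 (baseline) cognition and empowerment scores as covariates. Check Table 1 so that it agrees. Section 4.4.1 can stay as it is.

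The cost is one phrase in 4.4.2 and one sentence in 6.2.2. Families have two fewer procedures at the make-up visit, and the GMFM-66 and the other outcomes are still measured there. The loss is that no cognition or empowerment score is taken right after make-up treatment.
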